
regulate expression of numerous genes. Interestingly, digoxin does not alter PKM2 kinase activity but suppresses PKM2 dependent transcriptional activity. This area is significant because sterile inflammation (SI) is the central pathological process in AH. Our results identify PKM2 as a key molecule in liver sterile inflammation which can be therapeutically targeted. The identification of digoxin as a PKM2 binder, which leads to critical anti-inflammatory effects, provides a novel opportunity to reduce liver inflammation in AH. We have further identified a unique molecular profile from a pilot aptamer-proteomic screen which will be expanded to the whole InTeam cohort to provide predictive markers for severe AH.

4. **Research Plan:** Summarize the study design and research procedures using non-technical language that can be readily understood by someone outside the discipline. **Be sure to distinguish between standard of care vs. research procedures when applicable, and include any flowcharts of visits specifying their individual times and lengths.** Describe the setting in which the research will take place.

Test if administering digoxin orally to healthy subjects results in a reduction in innate immune inflammatory responses in the peripheral blood.

We need to obtain peripheral blood lymphocytes from healthy subjects on different doses of digoxin to test if digoxin has an effect on the immune response of PBLs.

A) There will be three study groups.

Groups:

A: Placebo n=15

B: Digoxin 3 mcg/Kg/day n=15

C: Digoxin 0.15 mcg/Kg/day n=15

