B) The data management system will be set up in the University of Massachusetts Medical School secure REDCap environment, which is used for all of the pilot studies funded by NIAAA as part of the AlcHepNet Research Network. This HIPAA-compliant, 21 CFR Part 11 compliant environment is accessible only by medical school staff and collaborating clinical sites of the AlcHepNet who are assigned an account in this environment by UMMS IT with approval by the UMMS IRB. The system will be programmed for a single entry with validation rules at the time of entry and additional checking conducted after the data have been submitted to the main data base. These edits will check for validity, consistency, and normal range values. Edit queries will be generated and resolved by clinic staff with corrections posted to the database through the REDCap system, which enforces an audit trail for all changes. The study database will be stored in REDCap within the secure environment to protect any PHI/PII data

that are collected as part of the study. We will strive to minimize collection of such data and REDCap will be programmed to segregate that data from the study data so that exports for analysis will be deidentified. Data will be exported from REDCap for import into the latest version of SAS (SAS Institute, Cary, NC) or other statistical software for all analysis.

C-E) All reports and analyses will be generated from these files. Data files (and accompanying programs) that are used for reports, presentations, or publication will be archived as required past the end of the study. REDCap will also have the audit trail capability enabled for tracing any data modifications. Data from laboratories can be uploaded directly into REDCap for storage. The REDCap system will be programmed and maintained by study staff at the U Mass Medical School AlcHepNet Data Coordinating Center while data entry will be performed by study staff at the local site.

The sample size for this pilot study was based on results from in vitro experiments, where differences in as few as 5 participants were seen to be significantly different. Given the inherent variability in the absorption of digoxin in humans, a sample size of 15 was determined to be reasonable to provide a reasonable distribution of results from repeated measures of participants at the differing digoxin dose levels.

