- B. What are the conditions or procedures for sharing of materials and/or distributing for future research projects? *Write here*
- C. Is widespread sharing of materials planned? *Write here*
- D. When and under what conditions will materials be stripped of all identifiers? *Write here*
- E. Can donor-subjects withdraw their materials at any time, and/or withdraw the identifiers that connect them to their materials? *Write here*
 - i. How will requests to withdraw materials be handled (e.g., material no longer identified: that is, anonymized) or material destroyed? *Write here*
- F. Describe the provisions for protection of participant privacy *Write here*
- G. Describe the methods for the security of storage and sharing of materials *Write here*

6. **Subject Population:** Provide a detailed description of the types of human subjects who will be recruited into this study.
In total 60 healthy subjects ≥18 years and ≤70 years with no known clinical history will be recruited for this study.

7. **Subject classification:** Check off all classifications of subjects that will be specifically recruited for enrollment in the research project. Will subjects who may require additional safeguards or other considerations be enrolled in the study? If so, identify the population of subjects requiring special safeguards and provide a justification for their involvement.

 Children	 Healthy	 Fetal material, placenta, or dead fetus
 Non-English Speaking	 Prisoners	 Economically disadvantaged persons
 Decisionally Impaired	 Employees	 Pregnant women and/or fetuses
 Yale Students	 Females of childbearing potential	

NOTE: Is this research proposal designed to enroll children who are wards of the state as potential subjects?
 Yes No

8. **Inclusion/Exclusion Criteria:** What are the criteria used to determine subject inclusion or exclusion?

Inclusion Criteria

1. *Age >18 y ≤ 70 years*
2. *subjects with normal serum creatinine, normal EKG and currently not taking any medication.*

Exclusion criteria

1. *Autoimmune liver disease (ANA > 1/320)*
2. *Chronic viral hepatitis*
3. *Hepatocellular carcinoma*
4. *Complete portal vein thrombosis*
5. *Extrahepatic terminal disease*
6. *Pregnancy*

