The principal investigator (*[name]*) will conduct a review of all adverse events upon completion of every study subject. The principal investigator will evaluate the frequency and severity of the adverse events and determine if modifications to the protocol or consent form are required.

Please note: For any study that may be considered high risk, the IRB will be more focused on the safety requirements for the study and a DSMB will likely be required.

- d. For multi-site studies for which the Yale PI serves as the lead investigator:N/A
 - i. How will adverse events and unanticipated problems involving risks to subjects or others be reported, reviewed and managed? *Write here*
 - ii. What provisions are in place for management of interim results? *Write here*
 - iii. What will the multi-site process be for protocol modifications? *Write here*

13. Statistical Considerations: Describe the statistical analyses that support the study design.

Primary analyses of the biochemical measures will be conducted using mixed effects models to account for the correlation among the biochemical measures obtained from repeated blood draws on the same participant. The models will include digoxin dose (3 mcg/kg/day, 0.15 mcg/kg/day, none/placebo), time on study (weeks 0, 1, 2, and 3), and relevant patient characteristics (i.e., age, gender). A random intercept will be included so that each participant will have their own starting point and time will be a categorical predictor to better model a potential curvilinear relationship between time on study and biochemical levels without assuming a linear slope. Because treatment group is a three-level variable, we will first conduct a Type III multi-degree of freedom test to determine if any difference exists among the three groups and, if that is significant, conduct all pairwise comparisons to determine where the difference is. Because these tests are not independent, we will apply a Bonferroni correction to the critical p-value to reduce the possibility of a Type I error by chance alone. In this case, the critical p-value will be set at $0.05/3 = 0.017$ so that any p-value less than 0.017 will be declared statistically significant.

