Adherence analysis will be ascertained using pill counts for each participant at the weekly visits. For safety analyses, we will record any adverse events, both serious (SAE) and not, described by the participant at each weekly visit. Each AE will include a description of the AE/SAE, relatedness to digoxin, and resolution. These will be summarized by treatment group and, if there are three or more participants in any one group with a specific AE/SAE, we will conduct a statistical test (Likelihood Ratio Chi-Square) to determine any statistically significant difference among the treatment groups using the analogous approach as above to first test for any difference in the incidence of AE/SAE among the three treatment groups followed by conducting the three pairwise comparisons, again using the Likelihood Ratio Chi-Square. Because this is a safety analysis, the critical p-value is left at 0.05 for all comparisons to avoid increasing the probability of a Type II error.

SECTION II: RESEARCH INVOLVING DRUGS, BIOLOGICS, RADIOTRACERS, PLACEBOS AND DEVICES

If this section (or one of its parts, A or B) is not applicable, check off N/A and delete the rest of the section.

A. RADIOTRACERS

N/A

1. Name of the radiotracer: *Write here*
2. Is the radiotracer FDA approved? YES NO

If NO, an FDA issued IND is required for the investigational use unless RDRC assumes oversight.

3. Check one: IND# *Write here* or RDRC oversight (RDRC approval will be required prior to use)
4. **Background Information:** Provide a description of previous human use, known risks, and data addressing dosage(s), interval(s), route(s) of administration, and any other factors that might influence risks. If this is the first time this radiotracer is being administered to humans, include relevant data on animal models.
Write here
4. **Source:** Identify the source of the radiotracer to be used. *Write here*
5. **Storage, Preparation and Use:** Describe the method of storage, preparation, stability information, method of sterilization and method of testing sterility and pyrogenicity.
Write here

B. DRUGS/BIOLOGICS

N/A

1. If an **exemption from IND filing requirements** is sought for a clinical investigation of a drug product that is lawfully marketed in the United States, review the following categories and complete the category that applies (and delete the inapplicable categories):

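### Between-group safety inference is by p-value only, most naturally read as sitting behind a three-group test; at 15 per group the safety statement should rest on intervals against placebo

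*Combined protocol and SAP*

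**What the plan says.** The safety paragraph of Section I item 13 (Statistical Considerations) summarizes adverse events by treatment group and sets a trigger for testing: "if there are three or more participants in any one group with a specific AE/SAE, we will conduct a statistical test (Likelihood Ratio Chi-Square"). The order of testing is to "first test for any difference in the incidence of AE/SAE among the three treatment groups followed by conducting the three pairwise comparisons", described as analogous to the approach set out just before it. That earlier approach, for the biochemical measures, runs a three-group test and then, "if that is significant, conduct all pairwise comparisons to determine where the difference is". The condition is explicit there; the safety paragraph does not repeat it.

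On the significance level: "Because this is a safety analysis, the critical p-value is left at 0.05 for all comparisons to avoid increasing the probability of a Type II" (a missed difference). The biochemical pairwise tests, by contrast, use 0.05/3 = 0.017.

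No confidence interval, risk difference, upper bound, assumed event rate or power for safety appears in the documents. Section I item 4 (Research Plan) lists 15 on placebo, "B: Digoxin 3 mcg/Kg/day n=15" and "C: Digoxin 0.15 mcg/Kg/day n=15". The size is justified in general terms: "a sample size of 15 was determined to be reasonable to provide a reasonable distribution of results from repeated measures".

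**The concern.** Two features combine. First, a p-value is the only between-group inference planned. With 15 per group, a non-significant result is compatible with a large digoxin excess, and without an interval the reader cannot see how large.

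Second, if the pairwise tests wait for a significant 2-df overall test, some digoxin-placebo differences that meet the plan's own 0.05 level will not be examined. That raises Type II error for the comparison that matters most for safety, while the plan gives not increasing Type II error as its reason for leaving 0.05 unadjusted.

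Participants are healthy volunteers, and Section V states that they get no direct benefit. A report of no significant difference among groups could be taken as more reassurance than the data support.

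**Working it through.** **Inputs.** From the documents: 15 per group (Section I item 4); trigger of three or more participants in one group, Likelihood Ratio Chi-Square, and 0.05 throughout (Section I item 13). Assumed: event rates, because the documents give none, and that the gate applies to safety. The plan offers no safety power to reproduce. Its one related figure, 0.05/3 = 0.0167, rounds correctly to 0.017.

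**Statistic.** G² = 2 Σ O ln(O/E), with zero cells contributing 0. The overall test has 2 df (critical value 5.99) and a pairwise test has 1 df (3.84).

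**Worked example, 0/1/3 events (placebo/low/high).**
- Overall: 4 events in 45, so E = 1.333 events and 13.667 non-events per group. G² = 2[1 ln(1/1.333) + 3 ln(3/1.333) + 15 ln(15/13.667) + 14 ln(14/13.667) + 12 ln(12/13.667)] = 4.64, p = 0.098.
- High versus placebo: E = 1.5 and 13.5. G² = 2[3 ln 2 + 12 ln(12/13.5) + 15 ln(15/13.5)] = 4.49, p = 0.034.

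| Events (placebo/low/high) | Overall p | High vs placebo p |
|---|---|---|
| 0/0/3 | 0.030 | 0.034 |
| 0/1/3 | 0.098 | 0.034 |
| 0/3/3 | 0.070 | 0.034 (same for low dose) |
| 1/2/6 | 0.057 | 0.025 |

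Only the first row passes the gate. In the third, placebo has no events and each digoxin group has three, yet no digoxin-placebo comparison follows.

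**Chance of missing the rise under the full rule, one dose group affected.** All 16³ outcomes of three Binomial(15, p) arms were enumerated. A detection requires the trigger, an overall p < 0.05, and a pairwise p < 0.05 with the dose group above placebo.

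| Placebo rate | 15-point rise | 20-point rise |
|---|---|---|
| 0% | 60% | 40% |
| 2% | 68% | 53% |
| 5% | 76% | 65% |
| 10% | 83% | 75% |

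**What the gate costs.** Chance of flagging high dose above placebo:

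| Rates (placebo/low/high) | With gate | Without gate | Cost, points |
|---|---|---|---|
| 0/0/20% | 60% | 60% | 0 |
| 5/5/20% | 24% | 30% | 6 |
| 10/10/30% | 25% | 31% | 6 |
| 5/15/25% | 31% | 42% | 10 |
| 10/25/40% | 40% | 52% | 12 |
| 0/10/20% | 42% | 60% | 18 |

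Costs are taken before rounding where the rounded columns differ by a point. With no placebo events the gate is free only if the low dose is also event-free; there the trigger of three is the binding limit.

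**What non-significant results leave open.**
- 0/15: exact upper 95% limit 1 − 0.025^(1/15) = 21.8%.
- 5/15 versus 1/15: pairwise p = 0.058; Newcombe 95% interval for the risk difference −3 to +52 points.

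**Sensitivity to group size.** Section I item 6 and the enrolment target in Section III give 60, not 3 × 15 = 45. At 60/3 = 20 per group the misses are 71% (5% to 20%), 69% (10% to 30%), 41% (0% to 15%) and 21% (0% to 20%).

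**The case against.** Several points on the other side stand.

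- **The gate is inferred.** The safety paragraph says only that the pairwise tests come after the overall one. The reference to the approach above makes a gate the more natural reading, not the only one. If no gate was meant, the wording still needs to say so.
- **The Type II sentence is modest.** A reader might infer that the plan promises a low miss rate. It does not: the sentence explains why no Bonferroni reduction is applied, and claims nothing about power.
- **Other safety outputs exist.** A reader might infer that the plan treats non-significance as proof of safety, or offers nothing else. The documents say neither. Events are summarized by group whatever the test shows, the investigator reviews all events as each subject completes (Section I item 12), and laboratory tests, ECGs and digoxin levels are checked weekly. These protect individuals and describe the data, but give no interval for excess risk by group.
- **No single miss rate belongs to the plan.** A figure of about 70-75% for a 15-20 point rise is tempting, because it is close to the 5% to 20% and 10% to 30% cases. It depends on a placebo rate the documents do not give; for events absent in placebo the miss is 60% or 40%.
- **The example is fragile.** For 3/15 versus 0/15 the Likelihood Ratio p is 0.034, but Fisher's exact p is 0.22 and the Newcombe interval is −4 to +45 points. The tests and the recommended intervals can disagree at small counts, which is a reason to rest the statement on the intervals.
- **The larger gate costs assume the low dose also raises the event rate.** The documents neither support nor exclude that. With the low dose at the placebo rate, the cost in the scenarios tried is 0 to about 6 points.
- **It is a pilot.** That is true, and it argues for estimation over sequential significance tests.

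**Conclusion.** The point holds in limited form and should be addressed. The planned between-group safety inference is by p-value only. On the natural reading it sits behind an overall test that can block digoxin-placebo comparisons meeting the plan's own 0.05 level.

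At 15 per group, with assumed placebo rates of 0-10% and one dose group affected, the full rule misses a 15-20 point rise about 40-83% of the time. The gate contributes 0 to about 18 points in the scenarios tried. The remainder is due to group size: without the gate, the miss at 5/5/20% is still about 70%. Dropping the gate therefore does not cure low power, and the missing intervals are the larger gap.

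All rates are assumptions. The calculations also assume that all 15 per group are analysed. Section I item 4 discards data from subjects removed under its stopping criteria and does not say whether that covers safety; if it does, the analysed numbers fall and event cases may be lost.

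**What to change.** Amend the safety paragraph of Section I item 13.

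1. **Intervals (main repair).** For every AE/SAE, tested or not, report the count and exact 95% interval per group, and the risk difference of each digoxin group versus placebo with a 95% interval (for example Newcombe). Base the safety statement on these intervals, particularly their upper limits, and state that p ≥ 0.05 is not evidence of no added harm.
2. **Gate.** For each event meeting the trigger, compare each digoxin group with placebo at 0.05 without requiring a significant overall test. Keep the three-group test as descriptive.
3. **Consistency.** Reconcile the enrolment of 60 with three groups of 15, and say whether removed subjects stay in the safety analysis.

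The cost is revised wording and a few table columns, with no new participants or data. The statistical price of item 2 is more false signals. At equal assumed rates in all groups, the chance per event of flagging either dose above placebo rises from 1.8% to 3.3% (5% rate), 3.4% to 7.1% (10%), 3.6% to 6.5% (15%) and 3.1% to 5.4% (20%). That fits the plan's stated preference not to increase missed harms.
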